6.3.2.2. Definition of a SAE

A serious adverse event is any untoward medical occurrence that, at any dose:

- a. Results in death
- b. Is life-threatening

NOTE: The term 'life-threatening' in the definition of 'serious' refers to an event in which the subject was at risk of death at the time of the event. It does not refer to an event, which hypothetically might have caused death, if it were more severe.

- c. Requires hospitalization or prolongation of existing hospitalization

NOTE: In general, hospitalization signifies that the subject has been detained (usually involving at least an overnight stay) at the hospital or emergency ward for observation and/or treatment that would not have been appropriate in the physician's office or out-patient setting. Complications that occur during hospitalization are AEs. If a complication prolongs hospitalization or fulfills any other serious criteria, the event is serious. When in doubt as to whether "hospitalization" occurred or was necessary, the AE should be considered serious.

Hospitalization for elective treatment of a pre-existing condition that did not worsen from baseline is not considered an AE.

- d. Results in disability/incapacity, or

NOTE: The term disability means a substantial disruption of a person's ability to conduct normal life functions. This definition is not intended to include experiences of relatively minor medical significance such as uncomplicated headache, nausea, vomiting, diarrhea, influenza, and accidental trauma (e.g., sprained ankle) which may interfere or prevent everyday life functions but do not constitute a substantial disruption.

- e. Is a congenital anomaly/birth defect
- f. Is medically important

NOTE: medical or scientific judgement should be exercised in deciding whether reporting is appropriate in other situations, such as important medical events that may not be immediately life-threatening or result in death or hospitalization but may jeopardize the subject or may require medical or surgical intervention to prevent one of the other outcomes listed in the above definition. These should also be considered serious. Examples of such events are invasive or malignant cancers, intensive treatment in an emergency room or at home for allergic bronchospasm, blood dyscrasias or convulsions that do not result in hospitalization, or development of drug dependency or drug abuse.

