7.3.1. Adverse Events of Special Interest

AESI have already been identified by the GSK Safety Review Team (SRT). This information will be provided for analysis purposes via an adjudication spreadsheet, and therefore, does not need to be re-derived from the raw data. For a broader description, see Appendix 10: PSAP Sections for AESI Reporting.

The reporting of AESIs is defined below.

An overall summary of the incidence of AESI will be tabulated, and presented by study year and "any time post-baseline". Rate of events per 100 person-years will also be reported. Further summaries of the preferred terms assigned to each AE special interest category will be provided.

A listing of all AESIs will be produced.

The categorizations for the adverse events of special interest groups are:

Malignant Neoplasms

- Malignancies Excluding non-melanoma skin cancer (NMSC)
- Malignancies Including NMSC
 - Solid Tumour
 - Hematologic
 - Skin (All)
 - NMSC
 - Excluding NMSC
- Tumours of unspecified malignancy adjudicated as malignant per GSK

Post-Infusion Systemic Reactions (PISR)

- PISR per Anaphylactic Reaction Customized MedDRA Query (CMQ) narrow search
- PISR per Anaphylactic Reaction CMQ broad search
- PISR per Anaphylactic Reaction CMQ algorithmic search
- Serious Anaphylaxis per Sampson Criteria per GSK adjudication
- Serious Acute PISR/Hypersensitivity per GSK adjudication
 - Serious Acute PISR Excluding Hypersensitivity per GSK adjudication
 - Serious Acute Hypersensitivity Reactions per GSK adjudication
- Serious Delayed Acute Hypersensitivity Reactions per GSK adjudication
- Serious Delayed Non-Acute Hypersensitivity Reactions per GSK adjudication

All Infections of Special Interest (All and Serious, separately)

- All opportunistic infections (OI) per GSK adjudication
- OI per GSK adjudication excluding Tuberculosis and Herpes Zoster
- Active Tuberculosis
 - Non-Opportunistic
 - Opportunistic
- Herpes Zoster
 - Non-Opportunistic
 - Opportunistic
 - Recurrent
 - Disseminated
- Sepsis

Depression*/suicide/self-injury (All and Serious, separately)

- Depression* (excluding suicide and self-injury)
- Suicide/self-injury
- Serious suicide/self-injury per GSK adjudication
 - Suicidal Behaviour
 - Completed Suicide
 - Suicidal Ideation

Self-injurious Behaviour without Suicidal Intent

Deaths

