11.10. Appendix 10: PSAP Sections for AESI Reporting

Section 15: Adverse Events of Special Interest

AESI are defined using preferred terms from the current version of MedDRA. The intent is to update these definitions semi-annually using the newest MedDRA version. Preferred terms used in the current and prior versions of MedDRA can be found in Section 17.

Section 15.1: Malignant neoplasms

Malignant neoplasms are identified using the sub-SMQs of Malignant or unspecified tumours (20000091), malignancy related conditions (20000092), haematological malignant tumours (20000227), non-haematological malignant tumours (20000228), haematological tumours of unspecified malignancy (20000229) and non-haematological tumours of unspecified malignancy (20000230) under the current version of MedDRA. The sub-SMQ of Malignant or unspecified tumours contains two further subcategories: "Malignant Tumours" and "Tumours of unspecified malignancy." Tumours of unspecified malignancy will be reviewed by GSK and identified as malignant or non-malignant for reporting.

Malignancies other than those in the "Tumours of unspecified malignancy" category will be categorized as hematologic, skin, or solid, based on a CMQ developed by the MAH (Section 17.1). In addition, the following customizations have been made (generally since MedDRA v19.1).

The following terms have been added as hematological tumour types:

Marginal zone lymphoma recurrent

Epstein Barr virus positive mucocutaneous ulcer

Primary gastrointestinal follicular lymphoma

Transformation to acute myeloid leukaemia

FIP1L1/PDGFR alpha fusion kinase positive

Acute bilineal leukaemia

Primary breast lymphoma

The following terms have been added as a solid tumour type:

Malignant meningioma metastatic

Astroblastoma

Langerhans cell sarcoma

Nasopharyngeal cancer metastatic

Phosphaturic mesenchymal tumour

Squamous cell breast carcinoma

Gleason grading score

Oncotype test

Malignant urinary tract obstruction

Sarcomatoid carcinoma

Cystadenocarcinoma pancreas

Paracancerous pneumonia

Chromophobe renal cell carcinoma

Gastrointestinal adenocarcinoma

Pleuropulmonary blastoma

Primary pulmonary melanoma

Dysplastic naevus

ALK gene rearrangement positive

Breast tumour excision

NMP22 test abnormal

The following terms have been added as a skin tumour type:

Naevoid melanoma

Trichoblastic carcinoma

The following terms have been added as a tumour of unspecified malignancy:

Mismatch repair cancer syndrome

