Skin neoplasm bleeding

Intestinal metastasis

Maternal cancer in pregnancy

Microsatellite instability cancer

Pulmonary tumour thrombotic microangiopathy

Tumour cavitation

Tumour hyperprogression

Paraneoplastic myelopathy

Carcinogenicity

BRAF V600E mutation positive

Paraneoplastic thrombosis

In addition, the preferred term "Malignant neoplasm progression" was moved from "Non-haematological Malignant Tumour" SMQ in MedDRA Version 20.1 to "Malignancy Related Conditions" SMQ in MedDRA Version 21.0, and was further customized to be a tumour of unspecified malignancy.

The following terms have been removed from the SMQ:

Paraneoplastic glomerulonephritis (as it is a complication of malignancy)

Lymphoma cutis

Mucinous cystadenocarcinoma of pancreas

Serous cystadenocarcinoma of pancreas

Secondary cerebellar degeneration

Bone marrow infiltration

Pseudoachalasia

Malignant exophthalmos

Tumour obstruction

Tumour psuedoprogression

Paraneoplastic arthritis

Tumour pruritus

Oncogenic osteomalacia

Neurogenic tumour

Non-melanoma skin cancer (NMSC) will be categorized using a CMQ developed by the Marketing Authorization Holder (MAH) (Section 17.1).

Note beginning with MedDRA v20.0 in 2017, there will be two new sub-SMQs of Hematological Malignancies. These do not result in any changes to how malignant neoplasms are identified.

Post-study malignancies that are captured in ARGUS prior to CSR approval, but are not captured in the clinical database, will be described within the CSR text but cannot be included in statistical post-text displays. Post-study malignancies are not adjudicated by the SRT.

Additionally, for the BEL115467 "BASE" study, any malignancies that are reported annually (in the Year 2-5 post-treatment follow-up) via malignancy status updates in the CRF and not captured in ARGUS, will not be adjudicated by the SRT.

Section 15.2: Post-infusion/injection systemic reactions

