spreadsheets to the study specific Medical Monitor, who adjudicates the non-serious events. Once updated, the spreadsheets are returned to the SRT central

• programming team and are used to create the SRT output for the next periodic instream review.

In addition, as part of individual study close-out procedures, the adjudications should be finalized as follows:

- Just preceding database freeze (DBF), allowing time to send queries or update the eCRF/database as necessary prior to DBF, and are used in the CSR.
- Between DBR and Source Database Lock (as required) to provide final confirmation of adjudications and ensure there are no new AESI or relevant data changes to adjudicated events since the pre-DBR adjudication. This would be a requirement for declaring database freeze (DBF).

Note, at study close-out, the study programming team is responsible for generating spreadsheets of AESIs based upon the clinical data, in consult with the SRT central programming team, and liaising with SERM to finalise the adjudication. Refer to the SRT team site for more information: SRT/Team Documents/SRT documentation/AESI/Belimumab ADAE AEANAL AESI Adjudication Variables Process.doc.

Section 16.1: Malignancies

All malignancies identified via the terms in Section 17.1 will be reviewed by GSK SRT. The classification of malignancies as solid tumor, hematological, and skin will be reviewed against the verbatim term to confirm an appropriate and accurate preferred term has been assigned, or to recommend follow-up with the investigator for additional specificity on the verbatim term. In addition, malignancies that are flagged more than once, e.g., based on a term for both a diagnostic procedure and a diagnosis, will be adjudicated as one event.

Tumors of unspecified malignancy, as identified per the terms in Section 17.1, will be reviewed clinically by the GSK SRT for reporting. In general, non-serious events in the tumours of unspecified malignancy with insufficient information will be categorized as not malignant. Serious adverse events with insufficient information will be categorized as either not malignant or malignant based on the type of tumor and likelihood the tumor type is malignant (e.g., thyroid nodules are common in SLE patients and are generally not malignant; tumor types with higher likelihood for malignancy would be assumed to be malignant).

Section 16.2: Serious hypersensitivity and post-infusion/injection systemic reactions

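### The malignancy list places a naevus and five test- or procedure-only terms under solid tumours, where no written rule allows a not-malignant decision

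*SAP*

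**What the plan says.** SAP Section 7.3.1 reports malignant neoplasms with and without non-melanoma skin cancer (NMSC), split into solid, haematological and skin tumours. It adds a separate line for tumours of unspecified malignancy, which alone is restricted to events adjudicated as malignant.

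The term lists are in SAP Appendix 10, which reproduces parts of the PSAP. PSAP Section 15.1 customises the standard query. Under "The following terms have been added as a solid tumour type" it names 20 terms, among them "Dysplastic naevus", "Gleason grading score", Oncotype test, ALK gene rearrangement positive, Breast tumour excision and NMP22 test abnormal.

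For the unspecified class, Section 15.1 says: "Tumours of unspecified malignancy will be reviewed by GSK and identified as malignant or non-malignant for reporting". For the other three classes, PSAP Section 16.1 says: "The classification of malignancies as solid tumor, hematological, and skin will be reviewed against the verbatim term". The stated aim there is to confirm that the preferred term is right or to ask the investigator for a more specific verbatim term. Section 16.1 also merges events flagged more than once.

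**The concern.** The two review routes can end differently. An event in the unspecified class is ruled malignant or not before it is counted. An event in the solid class has its coding and class checked and is then counted. That suits terms that name a cancer. It does not suit a term that names a naevus, a grading score, a gene test, a urine marker or an operation, because the coding can be perfectly correct with no cancer present.

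Long-term safety is the primary objective, and Protocol Section 1.3.1 says the drug's mechanism could raise malignancy risk. Under SAP Section 2.1 adverse events are pooled into one belimumab group so that they can be compared with the sponsor's other long-term studies. There is no concurrent control arm in which false positives would also appear. A misclassified event would also clash with the protocol's own view of cancer: in defining medically important serious events it says "Examples of such events are invasive or malignant cancers", so a non-serious naevus counted as a malignancy would be an anomaly.

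**Working it through.** The plan states no malignancy figure, so there is nothing to reproduce. The check compares lists and rules, followed by an illustration.

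**1. Count the terms.** The solid-tumour additions number 20. One is a naevus and five are tests or procedures: 1 + 5 = 6, and 6/20 = 30%.

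**2. Compare placement of similar terms.**

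| Kind of term | Solid list | Unspecified list |
|---|---|---|
| Skin lesion | Dysplastic naevus | Skin neoplasm bleeding |
| Gene marker | ALK gene rearrangement positive | BRAF V600E mutation positive |
| Test | Gleason grading score; Oncotype test; NMP22 test abnormal | – |
| Procedure | Breast tumour excision | – |

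Naevoid melanoma is in the skin list, so the naevus sits neither with skin tumours nor with terms awaiting a decision.

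**3. Follow one event through the rules.** Take a non-serious adverse event with verbatim and preferred term both dysplastic naevus.

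- As printed: it is flagged solid; the verbatim supports the preferred term; there is no duplicate; it is counted as a solid tumour. NMSC is nested under skin in SAP Section 7.3.1, so the event also enters malignancies excluding NMSC.
- If the term were in the unspecified list: it is reviewed clinically. Under Section 16.1 a non-serious event with too little information is in general classed as not malignant.

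The event is the same. Only list membership changes the outcome.

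**4. Illustrate the sensitivity.** SAP Section 7.2.2 defines the rate as 100 × events / subject-years. Two inputs are assumptions. The first is a true rate of 0.4 per 100 person-years, borrowed from the 0.4% in Protocol Section 1.3.1, which is a percentage of subjects in controlled trials and not a rate. The second is total person-years (PY), which the documents do not give. Expected events E = 0.004 × PY; one false event adds 100/PY to the rate and multiplies it by (E + 1)/E.

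| Assumed PY | E | Added per 100 PY | Multiplier |
|---|---|---|---|
| 200 | 0.8 | 0.50 | 1.8/0.8 = 2.25 |
| 400 | 1.6 | 0.25 | 2.6/1.6 = 1.63 |
| 600 | 2.4 | 0.17 | 3.4/2.4 = 1.42 |
| 1000 | 4.0 | 0.10 | 5.0/4.0 = 1.25 |

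**The case against.** A reader might infer that these terms escape review altogether. They do not. Section 16.1 has the Safety Review Team look at every flagged malignancy, Section 16 has the study Medical Monitor adjudicate non-serious events, and adjudications are finalised around database release and freeze. SAP Sections 7.3.1 and 11.5.3 take the reported events from the adjudication spreadsheet, with event-specific updates. A sensible reviewer could strike out a naevus. This stands, and it narrows the point to the written rule. Section 16 says adjudication follows the criteria it goes on to list, and for solid-list terms those criteria include no not-malignant outcome.

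Other replies also carry weight:

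- SAP Section 1 applies the PSAP version current at database release, so the printed list may be superseded.
- Protocol Section 6.3.2.1 says a procedure is not itself an adverse event, so the excision term should rarely arise.
- A test or procedure term in a subject with a real cancer is no false positive.
- Tables 2.40 and 2.49 show preferred terms and the listing shows verbatim text, so a naevus would be visible by name. The category totals in Tables 2.39 and 2.48 would still include it.

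It is also tempting to say that Paracancerous pneumonia should be deleted, because a paraneoplastic kidney term was removed as a complication of malignancy. The documents give that reason for one term only and keep other paraneoplastic terms for review. Deleting the flag could hide an underlying cancer.

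**Conclusion.** The point holds as a classification fault. Six of the 20 added solid terms default to a counted malignancy with no written route to a not-malignant decision, while comparable terms get one. The naevus is the clearest case. The documents do not describe it as benign, and the point does not need them to: the term names no cancer and is placed under solid tumours.

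A reader might go further and conclude that the malignancy count is small and inflated. The documents do not support that. They give no malignancy count, total sample size or person-years, and do not show that any such event occurred. The multipliers of 1.25 to 2.25 hold only under the assumed rate, the assumed 200 to 1000 person-years and one false event. They show that, if events are few, one default can move the rate materially. The change is worth making before reporting because it is cheap and affects a key safety outcome.

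**What to change.** In the PSAP version used at database release, move Dysplastic naevus, Gleason grading score, Oncotype test, ALK gene rearrangement positive, Breast tumour excision and NMP22 test abnormal to the unspecified class, so that each event is adjudicated before it is counted. Keep Paracancerous pneumonia flagged, but adjudicate it too. Terms that name a cancer stay where they are.

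Alternatively, add one sentence to PSAP Section 16.1 saying that any flagged term may be adjudicated not malignant. This leaves the lists alone and also covers marker-only terms elsewhere, such as the FIP1L1/PDGFR alpha fusion kinase term in the haematological list.

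With either option, footnote the change in the four malignancy tables. The cost is an edit to the term list or one sentence, and perhaps a few more events for an adjudication that already takes place. The drawback is comparability: the PSAP serves the whole programme, so counts may not match earlier long-term reports that used a previous list, which is why the footnote is needed.
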